## 1. SYNOPSIS

Study Title	Investigation of cerebrospinal fluid (CSF) pharmacokinetics of ondansetron
Brief Title	CSF PK of ondansetron
Objective	To determine human cerebrospinal fluid (CSF) and plasma pharmacokinetic parameters of 5HT3R antagonist ondansetron after intravenous administration.
Hypothesis	Approaches to enhance CNS penetration of ondansetron might be useful for obtaining analgesic effect with 5HT3R antagonists in neuropathic pain.
Study Period	Planned enrollment duration: Approximately 3 months Planned study duration: One (4-hour) study day per subject, on the day of knee/hip arthroplasty surgery.
Number of Subjects	15 evaluable subjects having elective hip or knee arthroplasty with spinal anesthesia from up to 30 consented subjects.
Study Treatment	Single intravenous 15-min infusion of 16mg ondansetron.
Study Design	Prospective, open-label, pharmacokinetic pilot study.
Inclusion and Exclusion Criteria	
Inclusion criteria:
 
 
1. Age between 18 and 70 years old;
 
2. Patients planned to undergo hip or knee arthroplasty with spinal anesthesia;
 
3. Ability to provide informed consent
 
 
Exclusion criteria:
 
 
4. Not giving consent to participate in the study;
 
5. Patients with history of or current hepatic or renal insufficiency;
 
6. Patients with <math>BMI \geq 33</math>;
 
7. Patients with heart failure or active arrhythmias;
 
8. Patients with severe systemic disease that is a constant threat to life;
 
9. Contraindication or allergy to ondansetron;
 
10. Pregnancy or lactation.
 
11. Prisoners
 

Measurements	
Ondansetron CSF and plasma Pharmacokinetics:
 
 
1. A single 4-mL CSF sample per subject.
 
2. Serial blood sampling at 0 (pre-infusion), 15, 30, 60, 120, and 180 min after ondansetron administration.
 
 
Genotyping: A blood sample will be obtained at baseline for determining the following single nucleotide polymorphisms (SNPs) as confounders of ondansetron PK parameters:
 
 
1. ABCB1 gene (p-Glycoprotein transporter): C3435T, G2677T, T-129C, G1199A, C1236T.
 

	2. In SLC22A1 gene (OCT1 transporter): R61C, C88R, G401S, M420del, G456R.
Statistical Methodology	
This is a pilot/feasibility study. Individual plasma concentration-time data will be analyzed using non-compartmental methods in Phoenix WinNonlin® 6.1, to determine ondansetron PK parameters such as volume of distribution (Vd), clearance (CL), maximum plasma concentration (Cmax), and the time to reach maximum concentration (Tmax).
 
A compartmental population-based PK model will be constructed, to determine the pharmacokinetic variables of ondansetron in CSF, and allow for the estimation of the partition coefficient between the plasma and CSF.

## 2. STUDY PROTOCOL

### 2.1 Background and Significance

Neuropathic pain [NeuP] affects 7-8% of the adult population and is particularly challenging to treat. More than 30% of neuropathic pain patients continue to suffer despite treatment; and there is clearly an urgent need for new treatment approaches. However, the translation of findings from current neuropathic pain animal models to clinical trials have been extremely disappointing, with multiple pre-clinically promising agents failing to show robust clinical effectiveness; suggesting that 1) additional pharmacodynamic (PD) and pharmacokinetic (PK) factors responsible for effective animal-to-human translation need to be considered, and 2) because of a large inter-subject variability in pain mechanisms and treatment response, an “all-comers” approach is suboptimal in yielding significant leaps forward in the success of treating neuropathic pain. Therefore, addressing possible PK and PD translational gaps and investigating genotypic and phenotypic predictors of response can improve the translational process and allow more effective drug discovery and individual analgesic tailoring in neuropathic pain.

Serotonergic 5HT3Rs in the central nervous system (CNS) have been identified as a promising pharmacological target in neuropathic pain [1, 2]. After peripheral nerve damage the character of serotonergic descending modulation changes from inhibitory to facilitatory through 5HT3Rs in the spinal cord [3, 4]. This finding is supported by studies demonstrating that intrathecal (IT) administration of 5HT3R antagonists such as ondansetron alleviates mechanical and thermal hypersensitivity in animal nerve injury models [1, 5]. In contrast to IT administration, systemic ondansetron does not produce consistent analgesia. However, this is not surprising, considering that CNS concentrations of 5HT3R antagonists such as ondansetron highly depend on the expression level of P-glycoprotein (Pgp) - an efflux transporter at the capillaries of the blood-brain barrier (BBB) which transports xenobiotics out of the CNS to the systemic circulation [6, 7].

Clinical trials performed with 5-HT3 antagonists for treating pain have yielded mixed results. Two studies with tropisetron in fibromyalgia have yielded somewhat positive results, but had methodological shortcomings, and a well-designed tropisetron study in 30 patients with low back pain was negative. Two studies with ondansetron in neuropathic pain were overall negative, but in one of the studies, pain reduction 2h after ondansetron administration was larger than with placebo [8, 9]. In both these studies individual data (personal communication with the authors) indicate that certain patients had good analgesic response to intravenous ondansetron, warranting further investigation into the individual response profiles.

We suggest that one of the caveats leading to unsuccessful clinical translation of the promising animal data is related to the essential pharmacokinetic criterion that probably determined the lack of efficacy of systemic ondansetron in rodents - i.e. inability to achieve effective concentration at the site of action. We propose that sufficient exposure of 5HT3R antagonists at their site of action in the CNS, as well as the choice of appropriate pain condition are of key importance for testing the clinical effectiveness of 5HT3R antagonists in NeuP. Consequently, the goal of the project is to establish detailed CNS pharmacokinetic (PK) parameters of ondansetron, to provide sound basis for a future study with enhanced CNS penetration of ondansetron in neuropathic pain.

Two genetic factors shown to affect the pharmacokinetics and the antiemetic efficacy of ondansetron are 1) polymorphism in the ABCB1 gene expressing P-glycoprotein, a transporter which controls the transport of ondansetron to the CNS via the BBB; and 2) polymorphism in the SLC22A1 gene expressing organic cation transporter-1 (OCT1), a transporter responsible for hepatic uptake of

ondansetron. We will collect the genetic data on these polymorphisms to account for inter-subject variability in pharmacokinetic parameters of ondansetron.

## 2.2 Preliminary Data

None

## 2.3 Objective

The primary objective of the study is:

To test the feasibility of:

1. Determining human cerebrospinal fluid (CSF) and plasma pharmacokinetics of 5HT3R antagonist ondansetron, after intravenous administration.
2. Determining single nucleotide polymorphisms in transporters involved in hepatic uptake (organic cation transporter-1 [OCT1]) and CNS disposition (P-glycoprotein) of ondansetron in human subjects.

## 2.4 Patient Selection

Overall, 15 evaluable subjects planned to undergo hip or knee arthroplasty with spinal anesthesia at Washington University / Barnes Jewish Hospital. We anticipate that we will need to consent approximately 30 subjects to achieve the enrollment goal.

### 2.4.1 Inclusion Criteria

Inclusion criteria:

1. Age between 18 and 70 years old;
2. Patients having elective hip or knee arthroplasty with spinal anesthesia;
3. Ability to provide informed consent

### 2.4.2 Exclusion Criteria

Subjects will not be enrolled if any of the following criteria exist:

1. Not giving consent to participate in the study;
2. Patients with history of or current hepatic or renal insufficiency;
3. Patients with  $BMI \geq 33$ ;
4. Patients with heart failure or active arrhythmias;
5. Patients with severe systemic disease that is a constant threat to life;
6. Contraindication or allergy to ondansetron;
7. Pregnancy or lactation.
8. Prisoners

The following ondansetron **contraindications** will disqualify subjects from participating:

1. Congenital QT syndrome
2. QTc interval  $>450\text{ms}$
3. Concomitant therapy with any of the following drugs:

- First generation **antipsychotic** medications Thioridazine, Haloperidol, Chlorpromazine, and Pimozide
- Second generation **antipsychotic** medications Ziprasidone and Quetiapine
- **Azole antifungals** Ketoconazole and Fluconazole
- **Antihistamine** Terfenadine,
- **Antidepressants** Trazodone, Citalopram, and Bupropion,
- **Antiarrythmics** Propafenone, Flecainide, and Procainamide
- **Fluoroquinolone** antibiotics Norfloxacin, Ofloxacin, and Ciprofloxacin
- **Macrolide** antibiotics Erythromycin and Azithromycin
- **Antiretrovirals** of Protease inhibitor (e.g. Ritonavir, Saquinavir) or Non-nucleoside reverse transcriptase inhibitors (e.g. Efavirenz, Zidovudine) family.
- **Cisapride**
- Other potent **inhibitors** of Cytochromes P450 **2D6** or **3A4**.

## 2.5 Design and Procedures

### 2.5.1 Study Design and Methodology

The potential subjects will be recruited from the Washington University / Barnes Jewish Hospital center for perioperative assessment and planning (CPAP) and the Washington University Orthopedics outpatient clinics, before their scheduled visit for elective knee or hip arthroplasty. Subjects may also be recruited from BJH Surgery Registration and the preoperative holding area on the day of surgery. Subjects who are potential candidates for the study will be provided with written and oral description of the study procedures, benefits, and potential risks. They will be given the opportunity to ask questions regarding the study. Informed consent will take place at Washington University/Barnes-Jewish Hospital medical center campus.

If agreeing to participate in the study, each subject will sign the informed consent document. Each subject who qualifies for entry into the study on the basis of inclusion/exclusion criteria and completion of informed consent will be assigned the next available patient number. This indicates enrollment in the study. In subjects with a history of or suspected renal or hepatic disorder, blood tests will be ordered following consent and reviewed prior to study participation for plasma creatinine, Alanine aminotransferase (ALT), Aspartate aminotransferase (AST) and albumin. Subjects with moderate or severe renal or hepatic failure will be excluded from the study at the discretion of the PI. Subjects with any history of cardiac arrhythmias will undergo 12 lead ECG to rule out QTc interval >450ms and will be excluded from the study.

Patients' demographic data will be recorded; height and weight will be measured for calculating BMI. Subjects who drop out of the study prior to completing the study will be replaced by using the next available subject number.

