### 2.5.2 Study Period

Subjects will be studied in the Department of Anesthesiology of Washington University-Barnes Jewish Hospital, prior to and during their scheduled hip or knee arthroplasty surgery.

An intravenous catheter will be inserted in an arm for drug administration and in the opposite arm for obtaining blood samples to evaluate the plasma concentrations of ondansetron. The former will be used also for pre/intraoperative fluids and anesthesia drug administration.

At baseline, a 5ml blood sample will be collected for pharmacokinetics and another 5ml sample for genetic analysis.

Ondansetron will be administered in a 16mg single dose as a 15 min intravenous infusion. Although up to 32mg doses of intravenous ondansetron have been used in clinical trials, 16mg is currently the highest FDA-recommended dose for single administration. Two additional 4mg doses of either IV or oral ondansetron will be allowed for postoperative nausea and vomiting treatment in the study subjects, at the discretion of the treating physicians.

A single CSF sample of 4ml will be collected immediately after spinal needle insertion and before administration of spinal anesthesia. This procedure is routinely performed in the holding area, approximately 30 min before the patient enters the operating room (OR) for planned surgical procedure with spinal anesthesia. As only one sample of CSF is obtained from each subject, the timing of the infusion will be scheduled at approximately 30, 60, or 120 min before planned pre-surgical spinal needle insertion. This will allow 3 time-points of CSF samples from the aggregate study cohort. For determination of the above timing, the patients will be randomized in blocks of 3 for infusion timing (approximately 5 subjects per block), to allow even distribution of CSF PK sample time-points.

Six 5mL serial venous blood samples will be obtained from all subjects at 0 (pre-treatment), 15, 30, 60, 120, and 180 min from the beginning of infusion in each patient, regardless of timing for CSF sampling. The samples will be put on ice, centrifuged for 10 min at 5000 rpm. Plasma will be transferred to two 1.5mL vials and stored at -80°C until analysis by HPLC-MS.

The CSF ondansetron pharmacokinetic profile will be constructed using population PK approach, according to the exact time of CSF sampling. Ondansetron concentration in plasma (expected 40-120ng/mL) and CSF (expected 3-12ng/ml) will be determined by HPLC-MS-MS analysis [10].

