### **2.5.7 Clinical Procedures and Laboratory Tests**

Due to the risk of QT interval prolongation with high doses of ondansetron, we exclude patients with QTc > 450ms, and any concomitant administration of drugs that increase the pro-arrhythmic risk with ondansetron. In addition, all subjects will be monitored with ECG for potential arrhythmias. However, it should be noted that ondansetron administration is standard of care in these patients. Blood hepatic function and renal tests will be performed and evaluated prior to study treatment for any subjects with suspected or known kidney and or liver disease.

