### **3.4 Procedures to Minimize Potential Risks**

Studies are conducted in the Washington University Clinical Research Center under the supervision of the PI and Co-investigators. The PI is trained and experienced in performing research in human subjects, and the co-investigators are board-certified anesthesiologists with extensive clinical and research experience in the perioperative setting.

Subjects are also continuously monitored by trained research (RN) nursing personnel throughout the study session and by their clinical team during surgery and recovery in the Post Anesthesia Care Unit (PACU), as a part of routine care. Subjects will be monitored by electrocardiogram for any potential cardiac abnormalities associated with ondansetron administration. Full patient monitoring and resuscitation capabilities are immediately available.

The 16mg dose of ondansetron, when infused over 15 minutes in adults 18-74 years old, was shown not to increase the QTc interval by more than 10ms, even if additional two doses of 8mg are administered later in the day [18]. Based on these data, and the current FDA recommendation, we will administer 16mg dose by 15-min infusion, and apply an upper age limit of 70 years on the study population.

Inclusion and exclusion criteria, monitoring, and the clinical protocol are designed to ensure that risks are absolutely minimal. Subjects are informed that participation is voluntary and they may refuse to participate and may withdraw from the study at any time without penalty. A pregnancy test will be performed on women of childbearing potential and subjects excluded if pregnant. Subjects will be told that in the event of a physical injury as the direct result of study procedures, they will be cared for by a member of the investigating team at no cost, within the limits of the Washington University compensation plan.

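### QTc above 450 ms disqualifies any subject, but 2.5.1 requires a pre-dose QTc only after an arrhythmia history; 2.5.1 also conflicts with 2.4.2 on organ function

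*Combined protocol and SAP*

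**What the plan says.** **QTc.** Section 2.4.2 lists ondansetron contraindications that "will disqualify subjects from participating". QTc above 450 ms is the second item, with no condition attached. Section 2.5.7 repeats it: "we exclude patients with QTc > 450ms, and any concomitant administration of drugs that increase the pro-arrhythmic risk with ondansetron". Section 2.5.1 ties entry to the criteria: "Each subject who qualifies for entry into the study on the basis of inclusion/exclusion criteria" and who completes consent receives a patient number and counts as enrolled.

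The one place that requires a QTc before dosing is also in 2.5.1: "Subjects with any history of cardiac arrhythmias will undergo 12 lead ECG to rule out QTc interval >450ms and will be excluded from the study". All subjects have ECG monitoring (2.5.2, 2.5.7, 3.4). Section 2.5.2 describes it as heart-rhythm monitoring on 4-lead monitors, during the infusion and for about 30 minutes after it.

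**Organ function.** The synopsis and 2.4.2 exclude past or present hepatic or renal insufficiency, with no severity grade and no discretion. Section 2.5.1 orders creatinine, ALT, AST and albumin when a renal or hepatic disorder is known or suspected. It then excludes moderate or severe failure, and leaves that to the PI's discretion.

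**Arrhythmia.** The synopsis and 2.4.2 exclude active arrhythmias. The 2.5.1 sentence quoted above refers to any history of arrhythmia.

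**The concern.** A numeric exclusion that applies to everyone needs a number for everyone. Here staff are told to exclude above a QTc limit, but for subjects without an arrhythmia history the protocol names no source for the value. Someone following the text exactly could dose a subject whom the text disqualifies.

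The organ-function conflict has a similar practical effect. A subject with past mild insufficiency fails 2.4.2 but may pass 2.5.1. Clearance is among the parameters to be estimated (2.5.4.2, 2.5.4.3), and 2.1 describes hepatic uptake of ondansetron, so who is admitted also matters for interpreting the results.

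**Working it through.** There is no planned figure to reproduce. The check is mainly a comparison of sections, with one piece of arithmetic on dose.

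**1. Who must meet the QTc limit?** Every subject: 2.4.2 and 2.5.7 set no subgroup, and 2.5.1 makes entry depend on the criteria. The threshold is the same, 450 ms, in all three sections.

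**2. Who must have a pre-dose QTc?** Under 2.5.1, only subjects with an arrhythmia history.

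**3. Does another section supply the value?**
- 2.5.2: 4-lead rhythm monitoring from the start of infusion. Eligibility has been settled by then.
- 2.5.7: ECG monitoring of all subjects, to watch for arrhythmias.
- 3.4: ECG monitoring for abnormalities associated with giving the drug.
- 4.2: comorbidity and medication data come from the subjects themselves. A QTc cannot be self-reported, and no chart ECG is named as a source.

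None of these requires a baseline QTc.

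**4. How are other measured criteria handled?** For body mass index, "height and weight will be measured for calculating BMI". For pregnancy, "A pregnancy test will be performed on women of childbearing potential and subjects excluded if pregnant". In each case a measurement is named for everyone to whom the criterion can apply. For QTc it is not.

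**5. How large is the risk?** Section 3.4 cites evidence that 16 mg over 15 minutes in adults aged 18 to 74 "was shown not to increase the QTc interval by more than 10ms", even with two further 8 mg doses. In this study, "Two additional 4mg doses of either IV or oral ondansetron will be allowed" after the 16 mg infusion.
- Dose in the cited evidence: 16 + 2 × 8 = 32 mg.
- Maximum allowed here: 16 + 2 × 4 = 24 mg.

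The permitted dose is 8 mg below the dose in that evidence. The evidence concerns the change in QTc, however. The protocol keeps a baseline limit as well, and applying that limit requires a baseline value.

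**6. Can the gap be sized?** No. That would need the share of subjects with an arrhythmia history, the share with an ECG on file, and the frequency of QTc above 450 ms. The documents give none of these.

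**7. Organ function.** Take a subject with a resolved history of mild renal insufficiency. Under 2.4.2 and the synopsis: excluded. Under 2.5.1: not moderate or severe, so not excluded, and any exclusion is discretionary. The two rules give different answers for the same person. Neither insufficiency nor failure is defined, so the text does not settle which rule was intended.

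**The case against.** The strongest reply is that history-triggered testing is this protocol's general screening model. Liver and kidney tests are ordered only when a disorder is known or suspected (2.5.1, 2.5.7), and the pregnancy test is limited to women of childbearing potential. On this view, asking for a QTc in every subject is a preference for universal over targeted screening. The parallel is fair but incomplete. The organ-function criterion is framed in terms of history and diagnosis, which a subject can report. The QTc criterion is a measured threshold that history cannot establish. If targeted screening was intended, the criterion should say so.

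Preoperative ECGs may also be routine for these patients. The documents do not say so, nor that they are reviewed. If they are on file, the fix costs almost nothing.

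The safety reply largely stands. Besides the dose comparison, the protocol uses a 15-minute infusion, caps age at 70, excludes congenital QT syndrome, active arrhythmias and interacting drugs, monitors rhythm and has resuscitation at hand. It also notes that ondansetron is routine in these patients.

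On organ function, 2.4.2 is the formal list and would normally govern. That settles precedence, but leaves a contrary working instruction in 2.5.1.

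A reader might infer from the literal wording of the arrhythmia sentence that no evaluable subject would have a protocol-required QTc, because everyone given the ECG is then excluded. The documents do not support building on that. It would make an ECG done to rule out a long QTc pointless, and the sentence most likely lacks a few words limiting exclusion to those above the limit. On that reading it is compatible with 2.4.2, and the defect is one of wording.

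**Conclusion.** The concern holds as a gap between a universal criterion and a selective measurement: the QTc limit can go unchecked in subjects without an arrhythmia history. This rests on the text alone, and assumes that no chart-ECG review is required in a document outside these. The risk is limited and no probability can be attached to it. A reader might infer that subjects face a substantial cardiac hazard, or that some will certainly be dosed above the limit. The dose evidence and the other safeguards argue against the first, and nothing in the documents establishes the second.

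The organ-function conflict is real and separate. No numerical effect on the PK estimates is claimed. The arrhythmia sentence is a minor wording matter on which the sponsor's intent is needed. None of this affects the sample size or the planned analyses, but it is worth correcting because the correction is cheap.

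**What to change.** **QTc (2.5.1).** Before infusion, check and document a QTc for every subject from a recent preoperative chart ECG, with the sponsor setting the window. If none is on file, obtain one routine 12-lead ECG. Exclude if QTc exceeds 450 ms.

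**Organ function.** Use one rule throughout. By default this is the 2.4.2 criterion, with the four blood tests used to confirm or rule out insufficiency. If the sponsor intended the narrower rule, amend 2.4.2 and the synopsis to match.

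**Arrhythmia sentence (2.5.1).** The sponsor should confirm whether only QTc above 450 ms, together with active arrhythmias under 2.4.2, is meant to exclude, and reword accordingly. If any arrhythmia history is meant to exclude, 2.4.2 and the synopsis need changing instead.

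**Cost.** Protocol wording, an occasional extra ECG, and possibly a few more screen failures among the up to 30 consented subjects. For those recruited on the day of surgery, the ECG must be done before the infusion, which is scheduled about 30, 60 or 120 minutes before spinal needle insertion. That is a scheduling constraint to plan for.
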